6.5 Dose escalation and dose modification

No dose escalations or dose modifications are allowed with fulvestrant.

No dose escalation will be allowed for alpelisib as alpelisib is to be started at the maximum recommended daily dose according to the SmPC. For participants who do not tolerate the protocol-specified dosing schedule, dose interruptions, and/or reductions are either recommended or mandated in order to allow participants to continue the trial treatment. Dose modifications are summarized in [Table 6-3](#) “Criteria for dose reduction / interruption and re-initiation of alpelisib for adverse drug reactions”. A maximum of 2 dose reductions will be allowed after which treatment must be discontinued as indicated in [Table 6-4](#) “Dose Reduction Steps for Alpelisib”. Deviations to stepwise dose reductions are not allowed.

These dose changes must be recorded on the appropriate eCRF

AEs for alpelisib are graded according to CTCAE v4.03 since this version is more objective with regard to hyperglycemia grading since it is based on laboratory values. Clinical judgment of the investigator, including confirmation of laboratory values if deemed necessary, should guide the management plan of each participant based on individual benefit/risk assessment.

After treatment is resumed at a lower dose:

- If the same toxicity reoccurs with the same severity, then the next treatment re-initiation must resume at a lower dose irrespective of duration, except if specified in [Table 6-3](#) “Criteria for dose reduction/interruption and re-initiation of alpelisib for adverse drug reactions”.
- Once the alpelisib dose has been reduced by the investigator, no re-escalation is allowed, even upon resolution of AE.

If a participant requires a withholding of alpelisib dose, the participant could continue fulvestrant, per investigator discretion. All scheduled assessments will continue to be performed as per protocol.

Permanent treatment discontinuation is mandatory for specific events indicated as such in [Table 6-3](#) “Criteria for dose reduction/interruption and re-initiation of alpelisib for adverse drug reactions” or listed in [Section 9.1](#) “Discontinuation and completion”. These dose changes must be recorded on the appropriate eCRF.

Table 6-3 Criteria for dose reduction / interruption and re-initiation of alpelisib for adverse drug reactions

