Grade 4 (FG > 500 mg/dL) [≥ 27.8 mmol/L]	
 Omit alpelisib confirm fasting status of the assessment. If non-fasting, re-check within 24 hours. 
Regardless of fasting status, consider IV fluids.
 
 Exclude confounding factors like e.g. urinary tract infection. Consult with diabetologist, initiate or intensify medication with appropriate anti-diabetic treatment (see Grade 3), re-check within 24 hours. If grade improves then follow specific grade recommendations If FG is confirmed as > 500 mg/dL and confounding factors could be excluded, permanently discontinue participant from alpelisib.
CTCAE v 4.03 is modified to allow fasting blood glucose values in addition to fasting plasma glucose values. * For specific recommendations please see Section 6.5.1.3 "Guidelines for the treatment of alpelisib induced hyperglycemia"	
Investigations (Hepatic) . Note: this is for newly occurred or worsened from baseline	
Isolated total Bilirubin elevation	

Dose Modifications for alpelisib as specified below. Combination drug may be continued while alpelisib dose is being held, at the investigators discretion, and as specified.	
Worst toxicity - CTCAE Grade (value)	Dose Modifications for alpelisib
Grade 1 (> ULN - 1.5 × ULN)	
 No dose adjustment is required. Initiate appropriate medical therapy and monitor as clinically indicated.
Grade 2 (> 1.5 to 3.0 × ULN)	
 Interrupt dose until recovery to Grade ≤ 1 and resume at the same dose if resolved in ≤ 14 days or resume at the next lower dose level if resolved in > 14 days.
Grade 3 (> 3.0 to 10.0 × ULN)	
 Interrupt dose until recovery to Grade ≤ 1, then resume at the next lower dose level.
Grade 4 (> 10.0 × ULN)	
 Permanently discontinue.
Isolated AST or ALT elevation	
Grade 1 (> ULN - 3.0 × ULN)	
 No dose adjustment is required. Initiate appropriate medical therapy and monitor as clinically indicated.
Grade 2 (> 3.0 to 5.0 × ULN)	
 Interrupt dose until recovery to Grade ≤ 1, then decrease dose level.
Grade 3 (> 5.0 to 20.0 × ULN)	
 Permanently discontinue.

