16.2 Appendix 2: Liver event and laboratory trigger definitions & follow-up requirements

Table 16-4 Liver event and laboratory trigger definitions

	Definition/ threshold
Liver laboratory triggers If ALT, AST and total bilirubin normal at baseline:	
 · ALT or AST $> 5 \times$ ULN · ALP $> 2 \times$ ULN (in the absence of known bone pathology) · Total bilirubin $> 3 \times$ ULN (in the absence of known Gilbert syndrome) · ALT or AST $> 3 \times$ ULN and INR > 1.5 · Potential Hy's Law cases (defined as ALT or AST $> 3 \times$ ULN and Total bilirubin $> 2 \times$ ULN [mainly conjugated fraction] without notable increase in ALP to $> 2 \times$ ULN) · Any clinical event of jaundice (or equivalent term) · ALT or AST $> 3 \times$ ULN accompanied by (general) malaise, fatigue, abdominal pain, nausea, or vomiting, or rash with eosinophilia · Any adverse event potentially indicative of a liver toxicity*
If ALT or AST abnormal at baseline:	
 · ALT or AST $> 2 \times$ baseline or > 300 U/L (whichever occurs first)

*These events cover the following: hepatic failure, fibrosis and cirrhosis, and other liver damage-related conditions; non-infectious hepatitis; benign, malignant and unspecified liver neoplasms ULN: upper limit of normal

Table 16-5 Follow up requirements for liver laboratory triggers with liver symptoms

ALT	TBL	Liver Symptoms	Action
ALT increase without bilirubin increase:			
If normal at baseline: ALT > 3 × ULN	Normal For participants with Gilbert's syndrome: No change in baseline TBL	None	
 No change to trial treatment 
 Measure ALT, AST, ALP, GGT, TBIL, INR, albumin, CK, and GLDH in 48-72 hours. Follow-up for symptoms.
If elevated at baseline: ALT > 2 × baseline or > 300 U/L (whichever occurs first)			
 Interrupt trial drug 
 Measure ALT, AST, ALP, GGT, TBIL, INR, albumin, CK, and GLDH in 48-72 hours. Follow-up for symptoms. Initiate close monitoring and workup for competing etiologies. Trial drug can be restarted only if another etiology is identified and liver enzymes return to baseline.
If normal at baseline: ALT > 5 × ULN for more than two weeks	Normal For participants with Gilbert's syndrome: No change in baseline TBL	None	
If elevated at baseline: ALT > 3 × baseline or > 300 U/L (whichever occurs first) for more than two weeks			

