If normal at baseline: ALT > 8 × ULN	Normal	None	
ALT increase with bilirubin increase:			
If normal at baseline: ALT > 3 × ULN	TBL > 2 × ULN (or INR > 1.5)	None	
If elevated at baseline: ALT > 2 × baseline or > 300 U/L (whichever occurs first)	For participants with Gilbert's syndrome: Doubling of direct bilirubin		
If normal at baseline: ALT > 3 × ULN	Normal or elevated	Severe fatigue, nausea, vomiting, right upper quadrant pain	
If elevated at baseline: ALT > 2 × baseline or > 300 U/L (whichever occurs first)			

Table 16-6 Follow up requirements for liver laboratory triggers

Criteria	Actions required	Follow-up monitoring
Total Bilirubin (isolated)		
> 1.5 to 3.0 ULN	
 Maintain treatment Repeat LFTs within 48 to 72 hours 	Monitor LFTs weekly until resolution ^c to ≤ Grade 1 or to baseline
> 3 to 10 × ULN (in the absence of known Gilbert syndrome)	
 Interrupt treatment Repeat LFT within 48 to 72 hours Hospitalize if clinically appropriate Establish causality Record the AE and contributing factors (e.g. conmeds, med hx, lab) in the appropriate CRF 	Monitor LFTs weekly until resolution ^c to ≤ Grade 1 or to baseline (ALT, AST, total bilirubin, Alb, PT/INR, ALP and GGT) Test for hemolysis (e.g. reticulocytes, haptoglobin, unconjugated [indirect] bilirubin)
> 10 × ULN	
 Discontinue the trial treatment immediately Hospitalize the participant Establish causality Record the AE and contributing factors (e.g. conmeds, med hx, lab) in the appropriate CRF 	ALT, AST, total bilirubin, Alb, PT/INR, ALP and GGT until resolution ^c (frequency at investigator discretion)
Any AE potentially indicative of a liver toxicity*	
 Consider trial treatment interruption or discontinuation Hospitalization if clinically appropriate Establish causality Record the AE and contributing factors (e.g., conmeds, med hx, lab) in the appropriate CRF 	Investigator discretion

^aElevated ALT/AST > 3 × ULN and TBL > 2 × ULN but without notable increase in ALP to > 2 × ULN

^b(General) malaise, fatigue, abdominal pain, nausea, or vomiting, or rash with eosinophilia

^cResolution is defined as an outcome of one of the following: (1) return to baseline values, (2) stable values at three subsequent monitoring visits at least 2 weeks apart, (3) remain at elevated level after a maximum of 6 months, (4) liver transplantation, and (5) death.

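### Table 6-3 and Appendix 2 give opposite alpelisib instructions in two liver-test bands, and no sentence says which governs interruptions and reductions

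*Protocol*

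**What the plan says.** **Bilirubin.** In Protocol Section 6.5, Table 6-3 covers isolated total bilirubin above 1.5 and up to 3.0 × ULN (Grade 2). The action is "Interrupt dose until recovery to Grade ≤ 1 and resume at the same dose if resolved in ≤ 14 days"; if recovery takes longer than 14 days, dosing resumes one level lower. A note limits the hepatic rows to elevations that are new or worse than baseline. Table 16-6 in Appendix 2 has a row for the same isolated range. Its action is "Maintain treatment", with "Repeat LFTs within 48 to 72 hours" and weekly monitoring until resolution.

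**ALT.** For isolated AST or ALT above 3 and up to 5 × ULN, Table 6-3 says "Interrupt dose until recovery to Grade ≤ 1, then decrease dose level". Table 16-5 has a row for ALT above 3 × ULN with normal baseline, normal bilirubin and no liver symptoms. Its action is "No change to trial treatment", with the retest instruction "Measure ALT, AST, ALP, GGT, TBIL, INR, albumin, CK, and GLDH in 48-72 hours".

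**Text that might rank them.** Section 6.5 presents Table 6-3 as the summary of dose modifications. It adds that "dose interruptions, and/or reductions are either recommended or mandated in order to allow participants to continue the trial treatment". It also says that "Permanent treatment discontinuation is mandatory for specific events indicated as such in" Table 6-3 or listed in Section 9.1.

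**The concern.** One laboratory result can meet both tables, and an investigator cannot carry out both instructions. Trial treatment includes alpelisib (Table 6-1), so leaving trial treatment unchanged is incompatible with interrupting alpelisib.

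Two things are at stake. The first is patient management. Following Appendix 2 keeps a participant on a drug that Table 6-3 stops. Following Table 6-3 in the ALT band uses a dose reduction that Table 16-5 does not call for. Only two reductions are allowed, and the dose may not be raised again. Much of this trial is run remotely, with results from local laboratories and decisions made by the investigator, so a single rule matters.

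The second is the classification of dosing deviations. SAP Table 5-1 defines O1 (wrong dose after a toxicity that triggers a modification) and O2 (toxicity that triggers an interruption) by reference to the protocol. In these two bands the protocol states two actions.

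**Working it through.** There is no planned figure to reproduce. The check is a row-by-row comparison, a search for a ranking sentence, and one small calculation.

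**1. Rows side by side**

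| Isolated elevation | Table 6-3 | Appendix 2 | Result |
|---|---|---|---|
| Bilirubin > 1.5 to 3.0 × ULN, new or worsened | Interrupt; same dose if resolved within 14 days, otherwise one level lower | Table 16-6: continue, retest | Opposite |
| Bilirubin > 3 to 10 × ULN | Interrupt, resume one level lower | Table 16-6: interrupt | Compatible |
| Bilirubin > 10 × ULN | Discontinue permanently | Table 16-6: discontinue | Same |
| ALT > 3 to 5 × ULN; normal baseline, normal bilirubin, no symptoms | Interrupt, then one level lower | Table 16-5: unchanged, retest | Opposite |

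The two higher bilirubin rows show that Table 16-6 does carry dosing actions. They agree with Table 6-3, so the lowest band stands out as the mismatch.

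**2. Limits of the overlap**

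- Bilirubin: eligibility allows values below 2 × ULN (Section 5.1, criterion 8). A participant who enters between 1.5 and 2 × ULN and stays there has nothing new or worsened. Table 6-3 does not apply, and there is no conflict.
- ALT: the Table 16-5 row needs a normal baseline, normal bilirubin and no symptoms. It names ALT only, so an isolated AST rise has no conflicting row there.

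**3. Search for a ranking sentence**

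- Section 6.5 directs the reader to Table 6-3 but does not mention the Appendix 2 liver tables.
- Its binding sentence covers permanent discontinuation, and neither band involves that.
- It describes interruptions and reductions as recommended or mandated without a general rule for which is which.
- Section 6.5.1.5 asks for a repeat test when aminotransferases exceed 3 × ULN. It gives no dosing rule for an isolated rise and does not cite Appendix 2.
- The body text's one pointer to an Appendix 2 (Section 6.2.2) concerns prohibited medication.

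No sentence ranks the tables for these bands.

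**4. Size of the lasting dose difference in the ALT band**

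Inputs: starting dose 300 mg/day and first reduction 250 mg/day (Table 6-4); at most two reductions and no re-escalation (Section 6.5).

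- Dose step from the starting dose: 300 − 250 = 50 mg/day; 50/300 = 16.7%.
- Reductions left after one event: 2 − 1 = 1 under Table 6-3; 2 − 0 = 2 under Table 16-5.

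In the bilirubin band the same step applies under Table 6-3 only if recovery takes more than 14 days.

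**The case against.** The best case for the plan is that it already assigns dosing to Table 6-3. Section 6.5 names that table as the place for dose modifications, its title covers reduction, interruption and re-initiation, and Section 4.5.1 sends the reader to Section 6.5 for dose adjustment. Appendix 2 is presented as trigger definitions and follow-up. Much of this stands: Table 6-3 is the likely intended source, and a careful investigator would probably use it. It is still not a precedence rule, because Tables 16-5 and 16-6 state treatment actions of their own, and in two bands those actions are the reverse.

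It is also fair to say that the practical weight is low. SAP Section 1 reports early termination for very low enrolment, and O1 and O2 remain in all analyses. That lowers the urgency but does not reconcile the text.

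A reader might infer more than the documents support, in four ways:

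- **That ALT above 5 × ULN is a third conflict.** Table 6-3 discontinues permanently there, and Section 6.5 makes such discontinuations mandatory, so Table 6-3 prevails.
- **That the extra exposure can be counted as the doses taken up to the 48 to 72 hour retest.** Neither Appendix 2 row says dosing stops at the retest, so such a count describes neither instruction.
- **That the correct dose cannot be known at all.** The pointer to Table 6-3 makes that too strong.
- **That Table 6-3 should also override the elevated-baseline rows of Table 16-5.** Those rows use thresholds relative to baseline, and ALT up to 5 × ULN is eligible with liver metastases. Replacing them would be a clinical dosing decision beyond the conflict shown here.

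**Conclusion.** The point holds for two bands only: new or worsened isolated bilirubin above 1.5 and up to 3.0 × ULN, and isolated ALT above 3 and up to 5 × ULN with normal baseline ALT, normal bilirubin and no symptoms. It is a minor internal inconsistency with a safety aspect.

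Its size per participant is an interruption made or not made. In the ALT band there is also one lasting dose level, 16.7% from the starting dose, and one of the two permitted reductions. The documents give no frequency for these elevations, so no number of affected participants can be stated. They also do not say whether anyone was still on treatment when the study ended. No estimate is affected, since SAP Section 1 says the data will only be listed.

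The conclusion rests on reading the action entries in the row where they appear. For both conflicting rows the action stands directly with its criterion in the available text.

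**What to change.** - State in Section 6.5, and again at the head of Appendix 2, that Table 6-3 governs alpelisib dosing in these two bands and that Appendix 2 governs retesting and work-up.
- In the Table 16-6 row for bilirubin above 1.5 and up to 3.0 × ULN, replace the instruction to continue with a reference to Table 6-3 for new or worsened elevations. Keep the 48 to 72 hour retest and the weekly monitoring.
- In the Table 16-5 normal-baseline row for ALT above 3 × ULN, replace the no-change instruction with a reference to Table 6-3. Keep the retest panel.
- Leave the elevated-baseline rows of Table 16-5 as they are.

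The cost is amendment wording, with no added visits, procedures or participants. If nobody remains on treatment, it is enough to record, where O1 and O2 are assigned, that Table 6-3 is the reference for these two bands.

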5.1 Inclusion criteria

Participants eligible for inclusion in this trial must meet **all** of the following criteria:

1. Participant is an adult ≥ 18 years old at the time of consent
2. Participant with ABC (locoregionally recurrent or metastatic) not amenable to curative therapy.
3. Participant with a histologically and/or cytologically confirmed diagnosis of ER-positive and/or PR-positive breast cancer by local laboratory.
4. Participant with a confirmed HER2-negative ABC.
HER2-negative defined as a negative *in situ* hybridization test or an immunohistochemistry status of 0, 1+ or 2+. If immunohistochemistry is 2+, a negative *in situ* hybridization (Fluorescence *In Situ* Hybridization, Chromogenic *In Situ* Hybridization, or Silver *In Situ* Hybridization) test is required by local laboratory testing.
5. Participant with a pathology report confirming PIK3CA mutant status by a certified laboratory using a validated PIK3CA mutation assay (from either tissue or blood).
It is recommended the tumor sample is collected after the most recent progression or recurrence.
6. Participant had progression of disease during or after endocrine-based therapy.
Aromatase inhibitor therapy does not need to be the latest treatment regimen.
7. Participant has a Performance Status at screening and at Cycle 1, Day 1 visit lower than or equal to 1 (ECOG/WHO PS ≤ 1)
8. Participant has adequate bone marrow and organ function as defined in the following laboratory valued (as assessed by site laboratory for eligibility):
 - Absolute neutrophil count $\geq 1.5 \times 10^9/L$
 - Platelets $\geq 100 \times 10^9/L$
 - Hemoglobin $\geq 9.0 \text{ g/dL}$
 - Calcium (corrected for serum albumin) and magnesium within normal limits or \leq Grade 1 according to National Cancer Institute (NCI)-CTCAE version 4.03 if judged clinically not significant by the investigator
 - International normalized ratio (INR) ≤ 1.5

- Creatinine Clearance ≥ 35 mL/min using Cockcroft-Gault formula
- Total bilirubin $< 2 \times$ upper limit of normal (ULN; any elevated bilirubin should be asymptomatic at enrolment) except for participants with Gilbert's syndrome who may only be included if total bilirubin is $\leq 3.0 \times$ ULN or direct bilirubin $\leq 1.5 \times$ ULN
- Potassium within normal limits, or corrected with supplements

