- In absence of liver metastases, alanine aminotransferase (ALT) and aspartate aminotransferase (AST) $< 3 \times$ ULN. If the participant has liver metastases, ALT and AST $\leq 5 \times$ ULN (elevated ALT or AST values must be stable for 2 weeks, without evidence of biliary obstruction by imaging)
- Fasting Serum amylase $\leq 2 \times$ ULN
- Fasting Serum lipase \leq ULN
- FPG ≤ 140 mg/dL (7.7 mmol/L) and Glycosylated Hemoglobin (HbA1c) $\leq 6.4\%$ (both criteria have to be met)

9. Participant is a man or a pre- or post-menopausal woman

Post-menopausal status is defined either by:

- Prior bilateral oophorectomy or
- Age ≥ 60 or
- Age < 60 and amenorrhea for 12 or more months (in the absence of chemotherapy, tamoxifen, toremifene, or ovarian suppression) and follicle-stimulating hormone (FSH) and/or estradiol in the post-menopausal range per local normal range. If patient is taking tamoxifen or toremifene and age < 60 , then FSH and plasma estradiol levels should be in post-menopausal range per local normal range.

Note: For women using therapy-induced amenorrhea other than ovarian radiation or goserelin, serial measurements (per local guidelines) of FSH and/or estradiol are needed to ensure menopausal status.

Pre-menopausal status is defined as either:

- Patient had last menstrual period within the last 12 months
OR
- If on tamoxifen or toremifene during the past 14 days, plasma estradiol and FSH must be in the premenopausal range per local normal range,
OR
- In case of therapy-induced amenorrhea, plasma estradiol and/or FSH must be in the premenopausal range per local normal range

10. Participant is willing to operate a smartphone including the telemedicine application and a medical device (glucometer)

11. Participant is willing to follow the requirements for remote participation.

12. Participant has signed ICF before any trial related activities and according to local guidelines.

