Grade 1 (FG > ULN - 160 mg/dL [> ULN - 8.9 mmol/L]) For participants with baseline values between > ULN - 140 mg/dL (ULN - 7.7 mmol/L) this applies only for values > 140 mg/dL (7.7 mmol/L)	
 Maintain dose level, and remind participant on lifestyle changes*. Start/intensify metformin as per guidance below or in cooperation with a healthcare expert experienced in hyperglycemia management or a diabetologist. 
Metformin 500 mg orally once daily with dinner. If no gastrointestinal (GI) intolerance after several days, increase to 500 mg bid, with breakfast and dinner. If tolerated, increase to 500 mg with breakfast, and 1000 mg with dinner. If tolerated, 1000 mg bid with breakfast and dinner. If not tolerated, reduce to prior tolerated dose.
 
Titrate to the MTD over a period of 3 weeks.
 
 Alternatively, consider starting an SGLT2 inhibitor alone or in combination with metformin, especially in participants at risk for developing severe hyperglycemia (See Section 6.5.1.3 "Guidelines for the treatment of alpelisib induced hyperglycemia"). Starting dose and titration should be in accordance with the local prescribing information and consistent with local practice. Monitor fasting glucose levels as clinically indicated and at least twice weekly for 8 weeks, then continue checking at least weekly until FG is within baseline values.

Dose Modifications for alpelisib as specified below. Combination drug may be continued while alpelisib dose is being held, at the investigators discretion, and as specified.	
Worst toxicity - CTCAE Grade (value)	Dose Modifications for alpelisib

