12.8 Sample size calculation

As this is a pilot trial to evaluate the use of DCT, there is no formal calculation of sample size. Approximately 20 participants will be included based on feasibility.

13 Ethical considerations and administrative procedures

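### Table 6-3's isolated liver rows set a recovery target below the ALT/AST or bilirubin at which some participants may enter, with no baseline alternative

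*Protocol*

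**What the plan says.** **Entry (Protocol 5.1, criterion 8).** Without liver metastases, ALT and AST must be below 3 × ULN. With them the limit is wider: "If the participant has liver metastases, ALT and AST $\leq 5 \times$ ULN", on condition that "elevated ALT or AST values must be stable for 2 weeks, without evidence of biliary obstruction by imaging". Total bilirubin must be below 2 × ULN, and "any elevated bilirubin should be asymptomatic at enrolment". In Gilbert's syndrome, total bilirubin up to 3.0 × ULN, or direct bilirubin up to 1.5 × ULN, is accepted.

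**Dose rules (Protocol 6.5, Table 6-3, hepatic rows).** A note on these rows says "this is for newly occurred or worsened from baseline". For isolated ALT/AST, Grade 2 (above 3.0 to 5.0 × ULN) carries the instruction "Interrupt dose until recovery to Grade ≤ 1, then decrease dose level", and Grade 3 (above 5.0 to 20.0 × ULN) means permanent discontinuation. For isolated bilirubin, Grade 2 (above 1.5 to 3.0 × ULN) and Grade 3 (above 3.0 to 10.0 × ULN) are both interrupted until Grade 1 or lower. Grade 1 ends at 3.0 × ULN for ALT/AST and at 1.5 × ULN for bilirubin. No row names baseline as an alternative target or makes an exception for Gilbert's syndrome.

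**Where the Protocol does use baseline.**
- The amylase/lipase row of Table 6-3 takes baseline as its recovery target.
- Section 6.5.1.5 lets the threshold for potential drug-induced liver injury depend on baseline ALT/AST and bilirubin.
- Appendix 2, Tables 16-4 and 16-5, sets ALT triggers for an elevated baseline as multiples of that baseline or 300 U/L. Restart after interruption requires enzymes back at baseline and another cause identified.
- Appendix 2, Table 16-6, maintains treatment at isolated bilirubin above 1.5 to 3.0 × ULN, monitors to Grade 1 or baseline, and excludes known Gilbert's syndrome from its row for above 3 to 10 × ULN.

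**The concern.** The Protocol deliberately admits some participants at Grade 2 for ALT/AST or bilirubin, then uses dose rules whose recovery target is a value those participants did not have at entry. The note on new or worsened values limits what triggers the rows. It does not alter the target. A participant whose value rises and then returns to its stable entry level has still not recovered under Table 6-3. The isolated hepatic rows set no maximum hold, so alpelisib stays off.

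The consequence is statistical as well as clinical. Under Section 8.4.3 a clinically relevant laboratory abnormality that requires action on trial treatment is recorded as an adverse event. A permanent stop for this reason would therefore enter the adverse-event discontinuation rate, a secondary endpoint meant to show whether remote management is safe and suitable. The glossary counts permanently stopping any trial drug as trial treatment discontinuation, and Section 9.1.1 withdraws such participants from the trial. Satisfaction, retention and PFS data could then be cut short by the entry value, not by the decentralized approach.

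**Working it through.** The Protocol gives no figure to reproduce here; "there is no formal calculation of sample size". The check compares thresholds. All values are multiples of ULN, and the example entry values and rises are illustrative.

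**Step 1: where the target lies below a permitted entry value.**

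| Group | Permitted entry | Target (Grade 1 or lower) | Entry range above target |
|---|---|---|---|
| ALT/AST, no liver metastases | < 3 | ≤ 3.0 | none |
| ALT/AST, liver metastases | ≤ 5 | ≤ 3.0 | > 3.0 to 5.0 |
| Bilirubin, no Gilbert's | < 2 | ≤ 1.5 | > 1.5 to < 2 |
| Bilirubin, Gilbert's (total) | ≤ 3.0 | ≤ 1.5 | > 1.5 to 3.0 |

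Every value in the last column is Grade 2 at entry.

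**Step 2: if *worsened* means a rise in value.** The fall below entry needed to restart is (entry − target) / entry.
- ALT 4.0 to 4.2 (0.2/4.0 = 5% rise): interrupted; (4.0 − 3.0)/4.0 = 25% below entry.
- Bilirubin without Gilbert's, 1.8 to 1.9 (0.1/1.8 = 6% rise): interrupted; (1.8 − 1.5)/1.8 = 17% below entry.

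**Step 3: if *worsened* means a rise in grade.** Neither case in step 2 triggers anything, because both stay in Grade 2. The cases caught are these:
- ALT 4.9 to 5.1 (0.2/4.9 = 4% rise): Grade 3, permanent discontinuation.
- Bilirubin with Gilbert's, 2.9 to 3.1 (0.2/2.9 = 7% rise): Grade 3, interrupted; (2.9 − 1.5)/2.9 = 48% below entry.
- Bilirubin without Gilbert's, 1.9 to 3.1 (1.2/1.9 = 63% rise): Grade 3, interrupted; (1.9 − 1.5)/1.9 = 21% below entry.

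On this reading a small rise suffices only near the top of the entry range. From ALT 4.0, passing 5.0 takes a rise of more than 1.0/4.0 = 25%. Without Gilbert's, bilirubin must go from below 2 to above 3.0, a rise of more than 50%.

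**Step 4: the same cases in Appendix 2.**
- For ALT 4.9 to 5.1, twice baseline is 2 × 4.9 = 9.8 × ULN, which is not reached. The 300 U/L limit is exceeded at 5.1 × ULN only if the local ULN is above 300/5.1 = 58.8 U/L. The documents give no ULN. Below that value this ALT rise alone meets neither elevated-baseline limit, while Table 6-3 requires a permanent stop.
- For bilirubin 1.8 to 1.9, Table 16-6 maintains treatment; on the value reading Table 6-3 interrupts.
- For Gilbert's bilirubin 2.9 to 3.1, the Table 16-6 interruption row excludes known Gilbert's; Table 6-3 interrupts.

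**Step 5: counter-check.** ALT 2.9 to 3.1 without liver metastases is interrupted, but the entry value of 2.9 already meets the target. A return to baseline allows restart, so this group is not affected.

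**The case against.** The strongest reply is that entry and dose rules do not contradict each other outright. A stable participant at 4 × ULN may enter and continue, because the note confines the rows to new or worsened values. That is correct, and a reader who inferred that such participants must be stopped at once would be wrong. Table 6-3 is also organised by worst CTCAE grade, and Section 12.5.4 counts a pre-existing event as emergent only if its severity increased. Both favour the grade reading, on which the quoted Grade 2 ALT/AST row never applies to someone who entered at Grade 2. This stands as far as it goes: the 25% and 17% figures depend on the value reading. The cases in step 3 do not.

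Other stronger readings are tempting but unsupported:
- *They can never restart.* They can, if the value falls below their own entry level to Grade 1. What does not suffice is a return to entry.
- *Entry at ALT 5.0 means a 40% fall before restart.* Any rise from 5.0 is Grade 3 and a permanent stop, so no restart arises.
- *The glucose row shows how to write the fix.* Its adjustment, beginning "For participants with baseline values between", changes only the Grade 1 trigger; recovery from Grade 3 stays at a fixed glucose value. The amylase/lipase row is the closer comparison within Table 6-3.
- *Ordinary laboratory variation will cause these stops.* The documents give no figure for such variation. Section 6.5.1.5 asks for repeat aminotransferase testing within 48 to 72 hours above 3 × ULN, and Section 6.5 leaves room for confirming values and for investigator judgement. Section 6.5 nevertheless makes the permanent discontinuations in Table 6-3 mandatory.

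Loss of follow-up is not certain either. The glossary and Section 9.1.1 point to withdrawal, but SAP 2.3.2.5 provides for alpelisib stopping while fulvestrant continues.

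Finally, SAP Section 1 reports early termination for low enrolment, with data to be listed only. That removes most of the effect on the reported rate but leaves the inconsistent instructions in the Protocol.

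**Conclusion.** The point holds for a limited group: participants with liver metastases who enter at ALT/AST above 3 to 5 × ULN, and those who enter with bilirubin above 1.5 × ULN. For them Table 6-3's target is below a permitted entry value, and on either reading of *worsened* some are caught by a rise of about 4 to 7%. At worst the result is a mandatory permanent stop (ALT 4.9 to 5.1) or a hold until bilirubin is 48% below entry (Gilbert's, 2.9 to 3.1). Appendix 2 gives different instructions for the same abnormalities, so this is a conflict and not only missing detail.

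The documents do not say how many participants fall in these ranges. With the planned 20, one such stop would move the adverse-event discontinuation rate by 1/20 = 5 percentage points. That describes the planned design only; it is not an effect to expect in the terminated trial's listings. The conclusion assumes the hepatic rows are applied as written. No view is taken on which clinical rule is right.

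**What to change.** Reconcile criterion 8, the isolated hepatic rows of Table 6-3 and Appendix 2 (Tables 16-4 to 16-6) for participants who enter above Grade 1. The text should say whether *worsened* means a rise in value or in grade, what reference defines recovery, and how Gilbert's syndrome is handled. The sponsor's clinical team decides which rule applies. Changing Table 6-3 alone would leave the conflict with Appendix 2 open.

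In the listing of discontinuations related to adverse events (SAP 2.5.1), flag stops in participants who entered with ALT, AST or bilirubin above Grade 1, and show the entry value beside the value at the stop. This fits the listing-only SAP.

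The cost is a footnote or aligned text in a protocol amendment, plus one listing flag, with no new tests. If the agreed rule refers to baseline, sites will have to look up the entry value when applying it. Because the trial has ended early, the amendment matters mainly if the Protocol is continued or reused; the flag is useful either way.
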